Each concomitant drug must be individually assessed against all exclusion criteria/prohibited medications and local prescribing information of azacitidine (Vidaza® (Azacitidine) USPI (2008)) and venetoclax (Venclexta® (Venetoclax) USPI (2020)). If in doubt, the investigator should contact the Novartis medical monitor before a participant starts treatment or allowing a new medication to be started. If the participant has already started treatment, contact Novartis medical monitor to determine if the participant should continue study treatment. Supportive therapy including prophylactic antibiotic and antifungal treatments, transfusions, growth factors (e.g. GCSF, ESA) etc. will be administered at the discretion of the investigators according to their local standard of care.

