8.3 Efficacy

8.3.1 Efficacy assessments

Disease response will be assessed locally by the investigator in all participants (MDS) according to modified IWG for MDS and WHO criteria (Cheson et al 2000, Cheson et al 2006, Arber et al, 2016, Platzbecker 2019). Response criteria are described in Table 8-2.

Investigators will assess and document response/progression at each time point as per the visit schedule. For efficacy analyses, baseline assessment is defined as the last non-missing assessment on or before the date of sabatolimab.

In addition, the hematological improvement per modified IWG-MDS criteria (Cheson et al 2006) will be assessed in all enrolled participants to report specific hematologic improvement (HI) of cytopenias in the three hematopoietic lineages: erythroid (HI-E), platelet (HI-P), and neutrophil (HI-N).

Response category	Definition [#]
Complete remission (CR)	Bone marrow:
	<= 5% blasts with normal maturation of all cell lineages. (Note: Persistence of dysplasia will be noted but does not preclude achievement of complete remission [CR])
	Peripheral blood:
	1. Hgb $\geq 10 \text{ g/dl}$ AND
	2. Platelets $\geq 100*10^9$ /L AND
	3. Neutrophils $\geq 1.0*10^9$ /L AND
	4. Blasts 0%
	(Note: the participant must not receive RBC or platelet transfusions, myeloid growth factor within 2 weeks before this disease assessment)
marrow Complete remission (mCR)	Bone marrow:

Table 8-2Modified response classification per IWG-MDS criteria (Platzbecker et
al 2019, Cheson et al 2006, Cheson et al 2000)

Response category	Definition [#]
	<= 5% blasts and blast count decrease by \geq 50% compared to baseline
	Peripheral blood/transfusion: Marrow CR may be achieved with or without improved blood counts or with or without transfusions
Partial remission (PR)	All CR criteria except
	Bone marrow: $\geq 50\%$ decrease from baseline in blasts in bone marrow AND blast count in bone marrow $> 5\%$
Stable Disease (SD)	Failure to achieve at least PR, but no evidence of progression for >8 weeks
Relapse from CR	Only in participants with a CR
	At least 1 of the following criteria is met: [in absence of another explanation not due to MDS, such as acute infection, bleeding, hemolysis, etc. Note that observation of peripheral blasts is not a sufficient criterion for relapse. However in that case, a bone marrow examination should be made to determine whether relapse has occurred]
	1. Return to baseline bone marrow blast percentage

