	2. Decrease of $\geq 50\%$ from maximum remission/response*** levels in neutrophils AND neutrophils $<1.0*10^{9}/L$. Note: neutrophils counts during periods of active infection will not be considered in determining the maximum
	3. Decrease of \geq 50% from maximum remission/response*** levels in platelets AND platelets < $100*10^{9}/L$
	4. Decrease from maximum remission/response*** levels in Hgb concentration by ≥ 1.5 g/dL AND Hgb < 10 g/dL
	5. Becoming transfusion dependent**
Disease progression	At least 1 of the following criteria is met:

Response category	Definition [#]
	[in absence of another explanation not due to MDS, such as acute infection, bleeding, hemolysis, etc. Note that observation of peripheral blasts is not a sufficient criterion for progression. However in that case, a bone marrow examination should be made to determine whether relapse has occurred]
	Bone marrow according to the number of blasts of the participant at baseline:
	1. Less than 5% blasts at baseline : \geq 50% increase in blasts over baseline to > 5% blasts
	2. 5% - < 10% blasts at baseline : \geq 50% increase over baseline to > 10% blasts
	3. $10\% - < 20\%$ blasts at baseline : $\ge 50\%$ increase over baseline to $> 20\%$ blasts.
	Participants with more than 20% of blasts will be considered to have transformation to acute leukemia per 2016 WHO classification (Arber et al, 2016)
	Peripheral blood:
	1. Decrease of $\geq 50\%$ from maximum remission/response*** levels in neutrophils AND neutrophils < $1.0*10^9/L$. Note: neutrophils counts during periods of active infection will not be considered in determining the maximum
	2. Decrease of \geq 50% from maximum remission/response*** levels in platelets AND platelets < $100*10^9/L$
	3.Reductionfrommaximumremission/response***levelsinHgbby2g/dLANDHgb $10g/dL$
	Becoming transfusion dependent**
	Occurrence of acute leukemia, or extramedullary leukemia per investigator's judgement

Modified Hematologic Improvement per IWG-MDS criteria (Cheson et al 2006)

Response category	Definition [#]
HI category	Definition [#] (HI must last at least 8 weeks)
Erythroid response (HI-E) (pretreatment*, <11 g/dL)	1. Hgb increase from baseline by \geq 1.5 g/dL, in at least 2 consecutive Hgb measurements and maintained over at least 8 weeks

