	2. Relevant reduction from baseline of units of RBC transfusions by an absolute number of at least 4 RBC transfusions/8 weeks compared with the pre-treatment transfusion number in the previous 8 weeks. Only RBC transfusions given for a Hgb of < 9 g/dL pre- treatment will count in the RBC transfusion response evaluation.
Platelet response (HI-P) (pretreatment*, <100 x 10 ⁹ /L)	1. Absolute increase from baseline of \geq 30 x 10 ⁹ /L for participants starting with $>$ 20 x 10 ⁹ /L platelets
	2. Increase from baseline from $< 20 \times 10^9$ /L to $> 20 \times 10^9$ /L and by at least 100% for participants starting with $< 20 \times 10^9$ /L platelets
Neutrophil response (HI-N) (pretreatment*, <1.0 x 10 ⁹ /L)	At least 100% increase and an absolute increase from baseline of $> 0.5 \text{ x } 10^9/\text{L}$

[#]If not defined otherwise, all of the criteria apply. Words that are written in italics highlights the modifications from the IWG criteria described in the reference publications.

**Pretreatment counts correspond to the baseline (not influenced by transfusions)*

**Definition of transfusion dependence and independence for red blood cells (RBC) and/or platelets are described below.

***maximum remission/response levels correspond to the best values reported in post baseline.

Transfusions Status Definitions for RBC/platelets

Transfusions for intercurrent diseases not due to study indication (e.g. bleeding, surgical procedure, hemolysis, infections) should not be taken into account for the following:

Transfusion dependence:

1. At baseline: participants having received ≥ 3 units of transfusion within the 8 consecutive
weekspriortobaseline.2. Post-baseline: participants having received ≥ 3 units of transfusion within any 8 consecutive
weeks during the course of the study ≥ 3 units of transfusion within any 8 consecutive

Transfusion independence:

1. At baseline: participants having received 0 units of transfusion within the 8 consecutive weeks prior to baseline.

2. Post-baseline: participants having received 0 units of transfusion within any 8 consecutive weeks during the course of the study.

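### HI requires a baseline free of transfusion effect but sets no transfusion or growth-factor condition on the qualifying on-study counts, so sustained support can be counted as response in ORR

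*Protocol*

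**What the plan says.** In Protocol Table 8-2 (Section 8.3.1), the CR entry carries a note that "the participant must not receive RBC or platelet transfusions, myeloid growth factor within 2 weeks before this disease assessment". PR takes over the CR criteria apart from the marrow blast item, so it carries the note too. Marrow CR is expressly independent of blood counts and transfusions.

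The HI block has two general conditions. One concerns the baseline: "Pretreatment counts correspond to the baseline (not influenced by transfusions"), with no time window. The other concerns duration: "HI must last at least 8 weeks". The lineage rules are then:

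- **HI-E item 1:** a hemoglobin rise of at least 1.5 g/dL, "in at least 2 consecutive Hgb measurements and maintained over at least 8 weeks".
- **HI-E item 2:** fewer RBC transfusions, "by an absolute number of at least 4 RBC transfusions/8 weeks compared with the pre-treatment transfusion number in the previous 8 weeks".
- **HI-P:** a platelet rise of at least 30 × 10⁹/L from a baseline above 20, or from below 20 to above 20 with at least a doubling.
- **HI-N:** "At least 100% increase and an absolute increase from baseline of" more than 0.5 × 10⁹/L.

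SAP Table 2-2 repeats these rules and footnotes. Protocol Section 6.2.1 permits supportive care on study, including that "growth factors (e.g. GCSF, ESA) etc. will be administered at the discretion of the investigators".

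ORR counts HI or better as best response (Protocol Table 2-1). SAP Section 2.5.1.2 derives best overall response centrally and accepts a single HI determination. Duration of response runs from the first CR, mCR, PR or HI (Protocol Section 12.5.1.2).

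**The concern.** HI is the one response category defined wholly by blood counts and transfusion need, so it is the category most open to supportive care. The written rule compares a baseline without transfusion effect with an on-study value that may be held up by transfusion, G-CSF or ESA. A participant without disease response could then be recorded as HI.

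That participant would enter the ORR numerator and the duration-of-response set. In someone who later reaches CR or mCR, a supported HI could also start the duration clock early. The issue remains live after the recruitment halt: SAP Section 1.2 keeps every endpoint except fatigue, and Section 2.6.1.1 reports ORR by dose level with exact intervals in small cohorts.

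**Working it through.** **1. The plan's own figures.** No target, power or sample size is given for ORR or HI. The only sizing rule is for CR: at least 36 of 70. It reproduces as an exact binomial tail:

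- P(X ≥ 36 | n = 70, p = 27/70) = 0.0195 (stated 0.020).
- P(X ≥ 36 | n = 70, p = 39/70) = 0.8005 (stated 0.800).

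These depend on CR alone, which carries the 2-week note, so nothing here changes them.

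**2. Conditions side by side (Protocol Table 8-2, SAP Table 2-2).**

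| Category | Baseline condition | On-study transfusion condition | On-study growth-factor condition |
|---|---|---|---|
| CR | none needed | none in prior 2 weeks | no myeloid growth factor in prior 2 weeks |
| PR | as CR, plus blast comparison | as CR | as CR |
| mCR | blast comparison | expressly waived | not stated |
| HI | not influenced by transfusion | none stated | none stated |

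**3. Illustrative records tested against the written HI rules.**

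- **HI-N, continued G-CSF.** Neutrophils 0.4 at baseline, at least 1.0 for 8 weeks. Increase 1.0 − 0.4 = 0.6, above 0.5. Relative increase 0.6/0.4 = 150%, above 100%. The rule is met.
- **HI-E, continued ESA.** If hemoglobin rises by 1.5 g/dL and RBC transfusions fall by 4 per 8 weeks, both items are met. This holds even if the table's footnote that all criteria apply unless defined otherwise is taken literally.
- **HI-P, repeated platelet transfusion.** Platelets 8 at baseline, kept above 20 for 8 weeks. Relative increase exceeds (20 − 8)/8 = 150%, above 100%. The two HI-P items cover different baseline ranges, so the footnote cannot require both.

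**4. What limits the HI-P route.** The same table lists new transfusion dependence as progression, and dependence is at least 3 units in any 8 consecutive weeks. Repeated transfusion of a participant not dependent at baseline would therefore be expected to meet progression. A participant already dependent at baseline does not become dependent, so the HI-P route stays open there.

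**5. Size per participant.** One misclassified HI-only participant adds 100/n points to ORR:

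- Cohort 1, planned n = 6: 100/6 = 16.7 points.
- Cohort 2, planned n = 12: 100/12 = 8.3 points.
- The 70 originally planned at 800 mg: 100/70 = 1.4 points.

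For scale, assume 6 responders of 12: 50.0% (exact 95% CI 21.1 to 78.9). One more gives 7/12 = 58.3% (27.7 to 84.8). The shift is visible but small beside an interval about 58 points wide.

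**The case against.** The strongest reply is that HI is the investigator's determination, not a mechanical count rule. SAP Section 2.5.1.2 says the investigator assesses response from marrow and blood data together with transfusions and myeloid growth factor in the last 2 weeks, and does not confine this to CR. This is real mitigation. But it states no rule that disqualifies HI and does not name ESA, so sites may differ and the derivation cannot check them.

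The 8-week duration also stands as a safeguard: a single transfusion or short G-CSF course does not qualify. And ORR is secondary and descriptive.

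Several stronger readings are tempting, and the documents do not support them:

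- **RBC transfusion alone yields HI-E.** Read literally, the footnote requires both items, and transfusing cannot produce the reduction in item 2. At least 3 units in 8 weeks is also progression for anyone not already dependent.
- **The venetoclax table (Protocol Table 6-6) shows the exposure.** It names G-CSF only after remission, when participants would generally already be ORR responders. Section 6.2.1 is the relevant permission.
- **Stopping support ends the response.** Duration of response ends at relapse, progression or death, not at loss of HI, and count-based progression requires no explanation other than MDS.
- **The inflation is about 17 points.** In the earlier sabatolimab plus HMA data (Protocol Section 4.6), 6 of 35 participants (17.1%) responded with HI only. That study did not use this triplet, and nothing shows that any of the six was on support.

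**Conclusion.** The gap is real and stands in both documents. The HI baseline is protected from transfusion effect; the qualifying on-study counts are protected from neither transfusion nor growth factor. Sustained G-CSF can meet HI-N and sustained ESA can meet HI-E. Repeated platelet transfusion can meet HI-P in participants already dependent at baseline.

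The consequence is possible misclassification in ORR and duration of response: 8.3 points of ORR per HI-only participant at n = 12 and 16.7 at n = 6. Both use planned cohort sizes. The total effect cannot be estimated, because the documents give no rate of G-CSF, ESA or platelet support and no rate of HI under such support. Only participants whose best response is HI can inflate ORR. The CR endpoint, its type I error and its power are untouched.

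**What to change.** Settle this in SAP Section 2.5.1.2 and Table 2-2, by one of two routes.

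1. **Rule in the derived best response and ORR.** Count HI-P and the hemoglobin part of HI-E only on values with no platelet or RBC transfusion, respectively, in the prior 2 weeks. Count HI-N only without myeloid growth factor in that window, and HI-E only without ESA. The ESA condition adds to the CR note, which covers myeloid growth factor only, so its window must be stated. Record the change in SAP Section 3.
2. **Sensitivity analysis.** Keep investigator-assessed HI as the main ORR. Add an ORR and a duration of response that exclude HI reached under support as defined in route 1.

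Both are analysis rules and ask for no change in supportive care. Protocol Section 6.2.1 already requires transfusions and medications to be recorded until the end of efficacy follow-up, so the cost is one table note and one programmed filter or flag. The downside is a possibly slightly lower ORR.

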8.3.2 Appropriateness of efficacy assessments

The assessment of response to study treatment is based on standardized criteria as proposed by modified IWG-MDS criteria (Cheson et al 2006) in Table 8-2.

8.4 Safety

Safety assessments are specified in Table 8-3 below with the assessment schedule detailing when each assessment is to be performed.

For details on AE collection and reporting, refer to AE section.

Assessment	Specification
Physical examination	A complete physical examination will include the examination of general appearance, skin, neck (including thyroid), eyes, ears, nose, throat, lungs, heart, abdomen, back, lymph nodes, extremities, vascular, and neurological. If indicated based on medical history and/or symptoms, rectal, external genitalia, breast, and pelvic exams will be performed.
	A complete physical examination is required at D1 of each cycle. At D8 of each cycle and D22 of Cycles 1 and 2, an abbreviated examination can be done at investigator's discretion.
	Information for all physical examinations must be included in the source documentation at the study site. Clinically relevant findings that are present prior to signing informed consent must be recorded on the appropriate CRF that captures medical history. Significant findings made after signing informed consent which meet the definition of an Adverse Event must be recorded as an adverse event.
Vital signs	Vital signs include blood pressure (supine position preferred when ECG is collected), pulse measurement, and body temperature.
Height and weight	Height in centimeters (cm) will be measured at Screening. Body weight (to the nearest 0.1 kilogram (kg) in indoor clothing, but without shoes) will be measured at screening and at subsequent timepoints as specified in Table 8-1

 Table 8-3
 Assessments and specifications

Performance status:

ECOG Performance status scale will be used as described in Table 8-4.

Grade	ECOG Status
0	Fully active, able to carry on all pre-disease performance without restriction
1	Restricted in physically strenuous activity but ambulatory and able to carry out work of a light or sedentary nature (e.g., light house work, office work)
2	Ambulatory and capable of all self-care but unable to carry out any work activities. Up and about more than 50% of waking hours
3	Capable of only limited self-care, confined to bed or chair more than 50% of waking hours
4	Completely disabled. Cannot carry on any self- care. Totally confined to bed or chair
5	Death

Table 8-4ECOG performance status

8.4.1 Laboratory evaluations

Local clinical laboratory parameters will be used for the analysis of scheduled hematology, chemistry and other blood specimens collected as part of safety monitoring (as detailed in Table 8-1 and Table 8-5) and the results will be collected in the eCRF.

Unscheduled assessments of these parameters can be performed more often as clinically indicated. It is preferable to use the same laboratory for all the assessments performed, especially for the hematology assessments.

A central laboratory will be used for the parameters listed in Table 8-6 and as per the schedule in Table 8-1.

Laboratory values obtained during the Screening phase will be used to assess participant's eligibility.

Novartis must be provided with a copy of the certification and a tabulation of the normal ranges and units for all local laboratories used in the trial.

Test Category	Test Name
Hematology	Hemoglobin (Hgb), white blood cells (WBC), differential (including basophils, eosinophils, lymphocytes, monocytes, neutrophils, bands, metamyelocytes, myelocytes, promyelocytes, blasts), atypical cells (e.g. LUC, erythroblasts), platelets

 Table 8-5
 Local clinical laboratory parameters collection plan

Test Category	Test Name			
	(absolute value preferred, %s are acceptable)			
Chemistry	Albumin, Alkaline phosphatase, ALT, AST, Gamma-glutamyl-transferase (GGT), Lactate dehydrogenase (LDH), Calcium, Magnesium, Phosphorus, Sodium, Potassium, Bicarbonate, Creatinine, Creatine kinase, Total Bilirubin, (Indirect Bilirubin, Direct Bilirubin)*, Total Cholesterol, Total Protein, Blood Urea Nitrogen (BUN) or Urea, Uric Acid, Amylase, Lipase, Glucose (fasting), Troponin-T or Troponin-I, NTproBNP**			
Virology***	HBsAg, HBcAb, HBV DNA (in participants positive for HBcAb), HCV RNA (PCR)			
	HIV (Only if required by local regulation)			
Coagulation	International normalized ratio [INR]), Activated partial thromboplastin time (APTT)			
Thyroid	At baseline: TSH, Free-T3 and Free-T4.			
	During treatment: TSH at timepoints indicated in Table 8-1 and as clinically indicated. If TSH is abnormal, then test free-T3 and free-T4.			
Urinalysis*** (dipstick)	Dipstick examination includes specific gravity, pH, glucose, protein, blood, bilirubin, ketones and WBC as clinically indicated. If urinalysis dipstick shows abnormalities, the site should perform a more detailed urinalysis follow-up as clinically indicated and per local practice.			
Pregnancy Test***	Serum / Urine pregnancy test (refer to Section 8.4.3 'Pregnancy and assessments of fertility')			
Additional Tests	Ferritin, iron, vitamin B12, erythrocyte and/or serum folates ****			

^{*} Indirect and direct bilirubin only required if total bilirubin is abnormal ** NTproBNP may be required as an additional test upon signs/symptoms and based on cardiology consult

Novartis	Confidential	Page 89 of 143
Amended Protocol Version 02 (Clean)		Protocol No. CMBG453B12203

*** Virology, urinalysis, and pregnancy test will only be reported in the source documentation **** Preferred method is erythrocyte folate but in case is not available then serum should be performed. However, every effort should be made to perform both test.

 Table 8-6
 Central clinical laboratory parameters collection plan

Test category	Test Name	
Cytokines	IFN-γ, IL-6, IL-1b, TNF-α	
Chemistry for DILI ¹	Glutamate dehydrogenase (GLDH)	

¹ at baseline and as clinically indicated for follow-up of DILI per Section 6.5.4.3

8.4.2 Electrocardiogram (ECG)

The ECGs are to be collected with ECG machines supplied by the central laboratory during the following timepoints: Screening, C1D1 predose, C1D8 post dose, and C3D8 postdose, EOT and unscheduled if clinically indicated. At the remaining time-points ECG will be collected locally (please refer to Table 8-7 and Table 8-8). The QT interval corrected by Fridericia's formula (QTcF) should be used for clinical decisions.

When triplicate ECG is required, collect three serial ECGs approximately 3 minutes apart after the participant has been resting comfortably in a supine position for about 10 minutes (it should be obtained before blood collection if a blood sample is scheduled at the same time point). Predose ECG to be collected prior to any study drug dosing. Post-dose ECG to be collected at the end of study drug infusion.

Cycle	Day	Time point *
Screening	Day -28 to Day -1	Anytime
Cycle 1	Day 1	Pre-dose ¹
	Day 8	Post-dose ²
Cycle 3	Day 8	Post-dose ²
ЕОТ	N/A	Anytime
Unscheduled	Any	As clinically indicated ³

 Table 8-7
 Central ECG collection plan

* all ECGs to be collected in 12-lead triplicate

¹ ECG collection prior to any study drug dosing

² ECG collection at end of sabatolimab infusion

³ Only required if clinically significant findings in local ECG

Table 8-8Local ECG collection plan

Cycle	Day	Time point *
Cycle 2	1	Pre-dose

Cycle	Day	Time point *
Cycle 3	1	Pre-dose
Cycle 4 and subsequent cycles	1	Pre-dose

Confidential

* all ECGs to be collected in 12-lead triplicate

Clinically significant ECG abnormalities present at screening should be reported on the appropriate CRF. New or worsened clinically significant findings occurring after informed consent must be recorded as adverse events. All ECGs recorded using the machines supported by the central ECG vendor must be transmitted electronically to the central ECG vendor and should be centrally reviewed by an independent reviewer. Any original ECG not transmitted electronically to the central laboratory should be forwarded for central review.

Any identifier details must be redacted e.g. participant initials, date of birth, where local regulations require it.

In case of QTcF prolongation, please refer to Section 6.5.4.4.

